5.1.1. Visit Windows

As participants do not always adhere to the protocol visit schedule, the following rules are applied to assign actual visits to analysis visits. Listed below are the visit windows and the target days for each visit. The reference day is Study Day 1. If a participant has 2 or more actual visits in 1 visit window, the visit closest to the target day will be used as the protocol visit for that visit window. The other additional visit(s) will not be used in the summaries or analyses but they can be used for determination of clinically important endpoints. If 2 actual visits are equidistant from the target day within a visit window, the later visit is used.

All assignments will be made in chronological order. Once a visit date is assigned to a visit window, it will no longer be used for a later time point except for the endpoint. Listed below (Table 2) are the analysis visit windows and the target days for each visit defined in the protocol.

Table 2: Visit Windows

Parameter	Analysis Period	Scheduled Visit Number	Time Interval (label on output)	Time Interval (Day)*	Target Time Point (Day)
Hematology,	Screening	1	Screening	<1	-57
Serum Chemistry	DB	2	Day 1	≤1	1
and Urinalysis		4	Day 29	2 to 43	29
		6	Day 57	44 to 71	57
		7	Day 85	72 to end of DB	85
		DB last	EW	2 to EW	
		visit			
	OLE ^b	OLE1	Baseline (OLE)	≤1	1
		OLE2	Month 1	2 to 47	31
		OLE3	Month 2	48 to 78	62
		OLE4	Month 3	79 to 138	93
		OLE5 to	Month 3 + 3*i	[138+90*(i-1)+1]	93+90*i
		OLE11 ^a		to [138+90*i]	
		OLE12	EW (OLE)	2 to EW (OLE)	
CCI	DB	2	Day 1	≤1	1
		4	Day 29	2 to 43	29
		7	Day 85	44 to end of DB	85
		DB last	EW	2 to EW	
		visit			
Physical	Screening	1	Screening	< 1	-57
examination,	DB	7	Day 85	72 to end of DB	85
Neurologic		DB last	EW	2 to EW	
examination,		visit			
Body weight					
	OLE ^b	OLE1	Baseline (OLE)	≤1	1
		OLE2	Month 1	2 to 47	31
		OLE3	Month 2	48 to 78	62
		OLE4	Month 3	79 to 138	93
		OLE5 to	Month $3 + 3*i$	[138+90*(i-1)+1]	93+90*i
		OLE11a		to [138+90*i]	
		OLE12	EW (OLE)	2 to EW (OLE)	
Brief neurological	DB	2	Day 1	≤1	1
examination		4	Day 29	2 to 43	29
		6	Day 57	44 to 85	57
	Screening	1	Screening	<1	-57

CONFIDENTIAL – FOIA Exemptions Apply in U.S.

		Scheduled			
	Analysis	Visit	Time Interval	Time Interval	
Parameter	Period	Number	(label on output)	(Day)*	Target Time Point (Day)
C-SSRS, Vital	DB	2	Day 1	≤1	1
signs		4	Day 29	2 to 43	29
		6	Day 57	44 to 71	57
		7	Day 85	72 to end of DB	85
		DB last	EW	2 to EW	
		visit			
	OLE ^b	OLE1	Baseline (OLE)	≤1	1
		OLE2	Month 1	2 to 47	31
		OLE3	Month 2	48 to 78	62
		OLE4	Month 3	79 to 138	93
		OLE5 to	Month $3 + 3*i$	[138+90*(i-1)+1]	93+90*i
		OLE11a		to [138+90*i]	
		OLE12	EW (OLE)	2 to EW (OLE)	
Electrocardiogram	Screening	1	Screening	<1	-57
	DB	4	Day 29	2 to 43	29
		7	Day 85	72 to end of DB	85
		DB last	EW	2 to EW	
		visit			
	OLE ^b	OLE1	Baseline (OLE)	≤1	1
		OLE2	Month 1	2 to 47	31
		OLE4	Month 3	79 to 138	93
		OLE5 to	Month $3 + 3*i$	[138+90*(i-1)+1]	93+90*i
		OLE11a		to [138+90*i]	
Seizure counts in	Baseline	Continuous	Baseline	<1	-56 to -1
e-diary	DB	collection	DB Period	1 to end of DB	1 up to 85
	FU		FU Period	End of DB to End	End of DB + 14
				of FU	
	OLE ^b		OLE Period	End of DB to End	End of DB + 730
				of OLE	

^{*}Relative to Study Day 1; DB=double-blind; EW=Early withdrawal; FU=Follow-up; OLE=Open-Label extension Footnotes:

5.2. Participant Dispositions

The number of participants in the following disposition categories will be summarized throughout the study by intervention group and overall:

- Participants randomized
- Participants who received study intervention during each phase (double-blind and open-label)
- Participants who completed the study during each phase (double-blind and open-label)
- Participants who discontinued study intervention during each phase (double-blind and openlabel)
- Reasons for discontinuation of study intervention during each phase (double-blind and openlabel)

a) Visits occur every 3 months after visit OLE4. To note, the "i" term is the iterator for the 3 monthly visits that occur after OLE4 e.g., i=1 for OLE5

b) Visit windows are as follows: +/- 5 days for OLE2, OLE3 and OLE4 and +/- 7 days for OLE5 and beyond (always to be calculated from OLE1); duration of 1 month is default 31 days until OLE4', duration of 3 months is default 90 days from OLE5 onwards

- Participants who terminated study prematurely during each phase
- Reasons for termination of study prematurely during each phase

Listings of participants will be provided for the following categories:

- Participants who discontinued double-blind study intervention
- Participants who discontinued open-label study intervention
- Participants who terminated study prematurely
- Participants who were randomized yet did not receive study intervention

The above summaries and listings will be provided for the randomized analysis set.

5.3. Primary Endpoint(s) Analysis

The primary efficacy endpoint will be evaluated at a 1-sided significance level of 0.05. For all other efficacy endpoints, no multiplicity adjustment will be done.

5.3.1. Definition of Endpoint(s)

The primary endpoint is the time to baseline monthly seizure count. The baseline monthly seizure count is an individualized measure and is defined as the number of observable focal onset seizures occurring during the 8-week baseline period, multiplied by 28/X_{BL}, where X_{BL} is the number of days comprising the participants baseline period. Seizure data on a given day are said to be missing if the participants report no seizures and also do not complete the reminder diary. For all participants, it will be assumed that no seizures occurred on the days where seizure data are missing in the e-diary because the majority of participants have more days where no seizures occcur, than days when a seizure occurred. Observable focal onset seizures include focal aware seizures with motor signs, focal impaired awareness seizures and focal to bilateral tonic-clonic seizures. Focal aware seizures without motor signs and other seizures will not be counted towards baseline monthly seizure count. Cluster seizures will be counted as a single seizure. The endpoint time to baseline monthly seizure count is defined, for each participant, as the number of days until the cumulative seizure count for the participant is equal to the baseline monthly seizure count, up to the end of the 12-week double-blind treatment period. Participants have the option to continue with the protocol having reached their baseline monthly seizure count in the double-blind period, however the primary analysis itself will not include seizure data beyond this point. For all subsequent analyses, seizure data collected during the entire DB period will be included.

5.3.2. Estimand

The primary estimand, the main clinical quantity of interest to be estimated in the study, is defined by the following 5 components:

Population: patients with established diagnosis of focal epilepsy (ILAE 2017 criteria) with 3 to 100 seizures per 28 days; currently on 1 to 4 AEDs with inadequate response to levetiracetam who have met the inclusion/exclusion criteria.

Variable: the number of days, until the patient experienced the number of seizures equal to baseline monthly seizure count, up to the end of the 12-week double blind treatment period.

Intervention event: the effect of the initially randomized treatment that would have been observed had all participants remained on their treatment throughout the double-blind treatment phase.

Intercurrent event (ICE): treatment discontinuation will be handled according to the hypothetical strategy as if the ICE would not have occurred. Similar efficacy is assumed for participants who had the ICE as those participants from the same treatment group who did not have the ICE.

Population-level summary: the difference in estimated hazard ratio between the treatments.

The primary analysis will be based on the full analysis set.

5.3.3. Analysis Methods

The intent-to-treat population will be the primary efficacy population. For each cohort, Kaplan-Meier analyses will be conducted to describe the time to reaching baseline monthly seizure count for each treatment group (JNJ-813 or Placebo) pooled over g

A formal comparison of time to monthly baseline seizure count will be made by estimating the hazard ratio and its 95% CI using a Cox proportional hazard regression model, including treatment and baseline CCI

Primary endpoint data from participants on placebo in subsequent cohorts will be combined with those from the previous cohort(s) if the Kaplan-Meier curves of the participants treated with placebo are comparable between cohorts. Where placebo groups are comparable, Kaplan-Meier curves for each cohort will be presented together to demonstrate comparability prior to combining the placebo groups.

Provided there are sufficient participants within each arm, additional sensitivity analyses will be undertaken to assess the robustness of the primary analysis to compliance with the intervention during the double-blind phase. Here the same analysis as the primary efficacy endpoint will be performed using the compliance analysis set (CAS). In addition, e-diary seizure reporting compliance will be summarized descriptively as defined in Appendix 7.

During Cohort 1, all participants and sites in Ukraine were impacted by the Russian invasion of Ukraine. To assess the impact of these data on the study, a sensitivity analysis on the primary efficacy endpoint will be performed where all Ukraine participants in Cohort 1 who were active in the study on or after 24th February 2022 (date invasion began) will be excluded.

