## Epilepsy related inclusion criteria

- 1. Participants must be men or women, 18 to 69 years of age, inclusive.
  - Note: Participants should be at least 18 years of age or older as per the legal age of consent in the jurisdiction in which the study is taking place.
- 2. Body Mass Index (BMI) between 18 and 35 kg/m^2 inclusive (BMI=weight/height). Minimum body weight should be 40 kg.
- 3. Criterion modified by Amendment INT-1

<sup>a This section has been amended by Amendment INT-2

b This section has been amended by Amendment INT-2 and 3

- 3.1 Criterion modified by Amendment INT-2
  - 3.2 Established diagnosis of focal epilepsy, using the International League Against Epilepsy (ILAE) criteria (Fisher 2017). Participants should not be enrolled if they are known to have had fewer than 3 or more than 100 seizures in any monthly period in the past 6 months. It is preferred that participants have experience in maintaining a seizure ediary.
- 4. Criterion modified by Amendment INT-1
  - 4.1 Must have had a neuroimaging procedure within 10 years, including a computed tomography (CT) scan or magnetic resonance imaging (MRI), that excluded a progressive neurologic disorder; these procedures may be performed within the 8-week baseline period.
- 5. Criterion modified by Amendment INT-2
  - 5.1. Criterion Modified by Amendment INT-3

5.2.

- 5.2.1. Cohort 1: Current treatment with at least 1 and up to 4 AEDs (including levetiracetam), administered at the appropriate dosage(s) and for a sufficient treatment period before screening. These AEDs must remain unchanged throughout the pretreatment and double-blind treatment periods (with the exception of dosage reductions of concomitant AEDs because of suspected elevated AED levels or side effects).
- 5.2.2. Cohort 2 and beyond: Current treatment with at least 1 and up to 4 AEDs (including levetiracetam or brivaracetam), administered at the appropriate dosage(s) and for a sufficient treatment period before screening. These AEDs must remain unchanged throughout the pretreatment and double-blind treatment periods (with the exception of dosage reductions of concomitant AEDs because of suspected elevated AED levels or side effects). Important note: screening of patients receiving Brivaracetam will start when enrolling for Cohort 2.

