#### 9.2. Efficacy analyses

#### 9.2.1. Primarya

The intent-to-treat population will be the primary efficacy population, which includes all participants who are randomly assigned to receive study drug and who have baseline and postbaseline seizure data. Data from participants on placebo in cohorts 2 and 3 will be combined with those from Cohort 1 if the Kaplan-Meier curves of the subjects treated with placebo are comparable between cohorts. The analysis for interim review may be done including both pooled and non-pooled placebo subjects.

The individualized baseline monthly seizure count is defined as the number of observable focal onset seizures occurring during the 8-week baseline period, multiplied by 28/ XBL, where XBL is the number of days comprising the baseline period. Observable focal onset seizures include focal aware seizures with motor signs, focal impaired awareness seizures and focal to bilateral tonic-clonic seizures. Focal aware seizures will not be counted towards baseline monthly seizure count.

\_

<sup>a This section has been amended by Amendment INT-1

The endpoint time to baseline monthly seizure count is defined, for each patient, as the number of days, until the patient experienced the number of seizures equal to baseline monthly seizure count, up to the end of the 12-week double-blind treatment period.

Although focal aware seizures with and without motor signs are entered in the e-diary, focal aware seizures without motor signs will not be counted in the analysis.

Kaplan-Meier analyses will be conducted to describe the time to baseline monthly seizure count distribution (with 95% CI) for each treatment group for all observable focal-onset seizures. A formal comparison of time to monthly baseline seizure count will be made by a Cox proportional hazard regression model, including factors for treatment and any other relevant covariates (details will be provided in the statistical analysis plan). Appropriate adjustment for multiple testing, in case of subsequent cohorts, will be detailed in the SAP.

The primary estimand, the main clinical quantity of interest to be estimated in the study, is defined by the following 5 components:

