#### 9.5. Data Review after each cohorta

After at least 55 patients in Cohort 1 and after at least 45 patients in Cohort 2 have completed at least 4 weeks of treatment, an interim unblinded review of all cumulative safety, PK, and efficacy data of JNJ-40411813 available to that date will be performed to decide on whether there should be any addition or modification to the dose(s) in the following cohorts and subsequent clinical studies. If the results of the review are inconclusive with respect to the assessment of efficacy, a second interim review of the same cohort may be done after the last participant has completed the 12-week visit. If safety concerns have been observed that are not expected to be solved by a dose reduction, the study will be stopped. This decision will be taken by an internal unblinded review committee. As a standard, data will be unblinded at the individual level (JNJ-40411813 vs placebo).

Completed cohorts may be unblinded for review by the sponsor members, if deemed necessary.

9

This section has been amended by Amendment INT-1, INT-3 and INT-4

The procedures for the internal interim review for Cohorts 1 and 2 will be documented in a separate charter.

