1.2. Study Design

This is a double-blind, randomized, parallel, placebo-controlled study with the option for an open-label extension (OLE) period. The study will consist of 1 to a maximum of 3 cohorts. In each cohort, for each participant the study consists of a screening visit, an 8-week prospective pretreatment baseline period, an up to 12-week double-blind treatment period and, for those participants electing not to enter the OLE period, a follow-up telephone visit 2 weeks after the last dose of study intervention. Participants have the option to enter an OLE period, in which treatment with JNJ-40411813 may be continued until the product becomes available by prescription, or until the development of JNJ-40411813 in this indication ceases. The total maximal duration of the study is approximately 22 weeks for each participant, up to the time of entry into the OLE period.

Participants from 18 to 69 years (inclusive) old with an established diagnosis of focal onset seizures will be enrolled in the study. For the first cohort, approximately 80 eligible participants will be initially enrolled to ensure that 60 participants are randomly assigned in a 2:1 ratio to receive either JNJ-40411813 twice daily (bid) or placebo. For each following cohort, approximately 60 eligible participants will be initially enrolled to ensure that 50 participants are randomly assigned in a 4:1 ratio to receive either JNJ-40411813 bid or placebo.

least 20% of the participants must be included in each of the two groups.

During the 8-week prospective pretreatment baseline period, participants will continue to take their prescribed AEDs (one of which must include levetiracetam or brivaracetam) without change in dosage(s); new concomitant AEDs should not be added. During the baseline period, participants will record seizure information (type and frequency of seizures) in an e-diary. Baseline monthly seizure count will be defined as the number of observable focal onset seizures recorded during the baseline period, multiplied by 28/ XBL, where XBL is the number of days comprising the baseline.

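### From Cohort 2 on, the primary Cox test pools earlier placebo once curves look 'comparable', and no final hazard ratio against concurrent placebo is prespecified

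*SAP*

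**What the plan says.** SAP 5.3.3 plans one formal primary comparison, a Cox model with treatment and a partly redacted baseline term. SAP 5.3 adds: "The primary efficacy endpoint will be evaluated at a 1-sided significance level of 0.05". For cohorts after the first, placebo data "will be combined with those from the previous cohort(s) if the Kaplan-Meier curves of the participants treated with placebo are comparable between cohorts". Protocol 9.2.1 sets the same condition. Neither document gives a test, a threshold, a decision-maker or a date for judging comparability.

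Some descriptive support is planned: "Where placebo groups are comparable, Kaplan-Meier curves for each cohort will be presented together to demonstrate comparability prior to combining the placebo groups". SAP 5.3.3 also plans Kaplan-Meier analyses for each cohort by treatment group.

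A non-pooled analysis is named only in Protocol 9.2.1, and only as an option at interim: "The analysis for interim review may be done including both pooled and non-pooled placebo subjects". The primary sensitivity analyses in SAP 5.3.3 are the compliance set and the exclusion of Ukraine participants in Cohort 1. Neither is restricted to concurrent placebo.

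SAP 1.2 plans Cohort 1 to "ensure that 60 participants are randomly assigned in a 2:1 ratio" and each later cohort to "ensure that 50 participants are randomly assigned in a 4:1 ratio". SAP 5.4 and 5.4.4.2 carry similar pooling rules to the secondary endpoints and to focal to bilateral tonic-clonic seizures.

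**The concern.** Participants randomised in an earlier cohort are not randomised controls for a later dose. If Cohort 1 placebo participants reached their baseline count faster than Cohort 2 placebo participants, the pooled hazard ratio overstates the drug effect. If they were slower, pooling can hide an effect. The planned curves would show such a shift by eye, but they give no concurrent hazard ratio or CI, so the reader cannot tell how far the primary result rests on the earlier controls.

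The documents give reasons why the cohorts may differ. The clearest is the population: "screening of patients receiving Brivaracetam will start when enrolling for Cohort 2" (Protocol 5.1, criterion 5.2.2). The war in Ukraine fell during Cohort 1 (SAP 5.3.3). The allocation ratio and the start of dosing also changed between cohorts, although both are weaker reasons for placebo outcomes to shift.

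Timing adds to this. Placebo curves by cohort can be drawn only with treatment codes open, and Protocol 9.5 allows that "Completed cohorts may be unblinded for review by the sponsor members, if deemed necessary". Without a fixed rule, comparability could be judged with results in view.

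**Working it through.** **Inputs.** 40:20 in Cohort 1 and 40:10 afterwards, one-sided 5%, 84 days of follow-up (SAP 1.2, 3, 5.3; Protocol 9.1). Stated power at 40:20 is 99% for a further 50% reduction and 83% for 30%; at 40:10 it is 94% for 50%. Event shares, drift and the meaning of comparable are not given, so they are assumed below and shown as ranges.

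**1. Which comparison do the plan's 94% describe?** Information scales with n1·n2/(n1+n2): 13.33 for 40:20, 8 for 40:10, 17.14 for 40:30 (pooled).
- 50% effect: z(0.99)+z(0.95) = 3.971. Times √(8/13.33) = 0.775 this is 3.077, and Φ(3.077−1.645) = 92.4%, close to the stated 94% (90.5-94.7% when the 99% is allowed its rounding).
- 30% effect: z(0.83)+z(0.95) = 2.599. At 40:10, Φ(2.599×0.775−1.645) = 64%. At 40:30, Φ(2.599×1.134−1.645) = 90%.

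So the stated 94% belongs to the concurrent comparison. For the smaller effect, pooling adds about 26 points of power that rest on earlier controls. The 99% and 83% cannot be reproduced independently, because the simulation's variance inputs are not given.

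**2. Share of earlier controls.** In Cohort 2, 20/(20+10) = 67% of pooled placebo is non-concurrent.

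**3. What can a 20 v 10 placebo check detect?**
- All 30 events: SE(log HR) = √(1/20+1/10) = 0.387. With HR 1.0 the 95% CI is exp(±1.96×0.387) = 0.47 to 2.14.
- 21 events (14+7): SE = 0.463, CI 0.40 to 2.48.
- If the rule were a two-sided 5% log-rank test, a true between-cohort HR of 2 is missed with probability 1−Φ(0.693/SE−1.96): 57% with 30 events, 68% with 21. At two-sided 10% it is 44% and 56%.

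**4. Size of the bias.** With no drug effect and a Cohort 1 placebo hazard 1.25 times that of Cohort 2, the pooled placebo hazard is roughly (10×1+20×1.25)/30 = 1.17, so the pooled HR is about 1/1.17 = 0.86. At 1.5 times it is about 1/1.33 = 0.75. Simulated medians among trials that pass the check are 0.86 and 0.76.

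**5. False positives of the whole rule** (pooled test if the check passes, concurrent test if not). Assumptions: exponential times censored at day 84, 70-95% of placebo participants reaching the event, no drug effect, one-sided 5% Cox Wald test, 10,000 trials per scenario.

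| Cohort 1 v Cohort 2 placebo hazard | Check passes (p>0.05) | False positives, p>0.05 | False positives, p>0.20 |
|---|---|---|---|
| 1.25 | 91-92% | 13-15% | 12-14% |
| 1.5 | 83-86% | 22-24% | 17-19% |

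With no drift the p>0.05 rule gives about 7%. The concurrent test gives 6-7%; its excess over 5% comes from the small, unbalanced arms. A repeat with log-rank tests and about 80% events gave 14% and 23%.

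**6. The same in seizure counts.** Daily over-dispersed counts, a 56-day baseline, eligibility of 3-100 seizures in each 28 days, and time to the cumulative baseline monthly count. Cohort 1 placebo reduction is 15% (the plan's figure). With Cohort 2 placebo assumed at 25% (30%), false positives are 10-16% (12-24%) over six variance settings, against about 7% concurrent. Reversed drift (25%, then 15%) gives 5-6%. No setting reproduced all three stated powers, so these figures are illustrative.

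**The case against.** The strongest objection is that the inflation is assumed. The documents support no particular drift, the p-value checks are stand-ins for an undefined rule, and the baseline for comparison is about 7%, not 5%, so the excess at 1.25 times is about 6-8 points. That is right. The figures show what the rule lets through, not what happened.

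Second, adding a concurrent estimate beside an unchanged pooled primary does not control that error. This also stands: the fix buys transparency.

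Third, protection exists. The endpoint is scaled to each participant's own baseline count, recruitment does not pause between cohorts, a Ukraine exclusion is planned, and per-cohort curves would show a material shift. These reduce the concern. They do not supply a concurrent hazard ratio, and scaling to baseline does not remove a difference in placebo response.

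Fourth, part of the Cox model text is redacted, and the interim short SAP (SAP 5.8.1) and the review charter (Protocol 9.5) are not public. A cohort term or an interim rule cannot be ruled out. The parallel wording in SAP 5.4.4.2 shows no cohort term. No passage says who judges comparability or when, so a judgement made with results in view is a possibility, not a documented event.

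Finally, the protocol treats secondary efficacy analyses as exploratory, and with 10 placebo participants a concurrent seizure-freedom odds ratio may not be estimable. The secondary-endpoint part of the fix therefore matters less.

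**Conclusion.** The concern holds. In the visible text, once placebo is pooled the primary result for Cohort 2 onward has no prespecified final Cox estimate against its own randomised placebo. If the curves were judged not comparable, the within-cohort test would follow by default, so the gap arises exactly when pooling occurs. Placebo groups of 20 and 10 cannot establish comparability, and even a tighter check (p>0.20) leaves false positives of 12-14% and 17-19% at the assumed drifts. Defining comparable is therefore not enough by itself. The allocation, the pooling rule and the 94% at 40:10 come from the documents; drift, event share and the form of the check are assumptions. The plan should be changed. Confidence is medium, because of the redaction and the unseen interim documents.

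**What to change.** In SAP 5.3.3, for Cohort 2 onward:

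1. Always report the Cox hazard ratio and CI against concurrently randomised placebo beside the pooled result, however the curves look. A single Cox model stratified by cohort, with a separate effect for each dose, does the same job, because each dose is then compared only with its own cohort's placebo.
2. Make no efficacy claim from the pooled result without showing the concurrent one.
3. State the rule for comparable before the Cohort 2 codes are opened for the final analysis.

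In SAP 5.4, say whether the per-cohort models use pooled or concurrent placebo, and add the concurrent model-based estimate where it can be estimated.

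The pooled analysis can stay primary. Making the concurrent comparison primary, or requiring the two to agree, would address the error rate but is the sponsor's choice.

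The cost is SAP wording and one extra model per endpoint, with no new data. The concurrent estimate is less precise: SE(log HR) is √(1/40+1/10) = 0.35 against √(1/40+1/30) = 0.24 with all events, or 0.37 against 0.25 with 90% events.
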